## 13.2. Assessing Adverse Events

In conjunction with the medical monitor, the Investigator will evaluate adverse events to ensure the events are categorized correctly. Elements of categorization will include:

- Seriousness/Classifications (see definition in Section 13.1).
- Causality or Relatedness i.e. the relationship between the test article, study treatment or study procedures and the adverse event (not related; unlikely related; possibly related; related see definition in Section 13.2.1).
- Adverse Event Severity Adverse event severity is used to assess the degree of intensity of the adverse event (mild; moderate; severe for all events see definition in Section 0).
- Outcome not recovered or not resolved; recovering or resolving; recovered or resolved with sequelae; recovered or resolved; death related to adverse event; unknown.
- Actions Taken none; temporarily discontinued; permanently discontinued; other.

#### 13.2.1. Causality Assessment

**Causality Assessment** – A determination of the relationship between an adverse event and the test article. The test article relationship for each adverse event should be determined by the investigator using these explanations:

- Not Related- An adverse event that is not related to the use of the test article, study treatment or study procedures.
- Unlikely Related An adverse event for which an alternative explanation is more likely, e.g. concomitant treatment, concomitant disease(s), or the relationship of time suggests that a causal relationship is not likely.
- Possibly Related An adverse event that might be due to the use of the test article, or to the study treatment or study procedures. An alternative explanation, e.g. concomitant treatment, concomitant disease(s), is inconclusive. The relationship in time is reasonable. Therefore, the causal relationship cannot be excluded.
- Related An adverse event that is listed as a possible adverse effect (device) or adverse reaction (drug) and cannot be reasonably explained by an alternative explanation, e.g.

concomitant treatment of concomitant disease(s). The relationship in time is very suggestive, e.g. it is confirmed by de-challenge and re-challenge.

## 13.2.2. Severity Assessment

**Severity Assessment** – A qualitative assessment of the degree of intensity of an adverse event as determined by the Investigator or reported to him/her by the subject. The assessment of severity is made irrespective of test article, study treatment or study procedure relationship or seriousness of the event and should be evaluated according to the following scale:

- Mild Event is noticeable to the subject, but is easily tolerated and does not interfere with the subject's daily activities.
- Moderate Event is bothersome, possible requiring additional therapy, and may interfere with the subject's daily activities.
- Severe Event is intolerable, necessitates additional therapy or alteration of therapy and interferes with the subject's daily activities.

## 13.3. Documentation and Follow-Up of Adverse Events

The recording and documenting of adverse events (ocular and non-ocular) begin when the subjects are exposed to the test article, study treatment or study procedure. Adverse events reported before the use of test article, start of study treatment, or study procedures will be recorded as medical history. However, if the condition deteriorates at any time during the study it will be recorded and reported as an AE. Untoward medical events reported after the subject's exit from the study will be recorded as adverse events at the discretion of the Investigator.

Upon finding an adverse event, the Principal Investigator will document the condition in the subject record and in the eCRFs. He/she will complete the Adverse Event /eCRF.

Complete descriptions of all adverse events must be available in the subject record. All Adverse Events including local and systemic reactions not meeting the criteria for "serious adverse events" shall be captured on the appropriate case report form or electronic data system. All adverse events occurring while the subject is enrolled in the study must be documented appropriately regardless of relationship.

It is the Investigator's responsibility to maintain documentation of each reported adverse event. All adverse events will be followed in accordance with applicable licensing requirements. Such documentation will include the following:

- Adverse event (diagnosis not symptom).
- Drawings or photographs (where appropriate) that detail the finding (e.g., size, location, and depth, etc.).
- Date the clinical site was notified.
- Date and time of onset.
- Date and time of resolution.
- Adverse event classification, severity, and relationship to test articles, as applicable.
- Treatment regimen instituted, including concomitant medications prescribed, in accordance with applicable licensing requirements.

- Any referral to another health care provider if needed.
- Outcome, ocular damage (if any).
- Likely etiology.
- Best corrected visual acuity at the discovery of the event and upon conclusion of the event, if related to the visual system.

In addition, if an infiltrate(s) is present, he/she will complete the Corneal Infiltrate Assessment eCRF. Where necessary, a culture of the corneal lesion will be collected to determine if the infection is microbial in nature. If cultures are collected, the date of culture collection and laboratory utilized will be recorded.

Changes in the severity of an AE shall be documented to allow an assessment of the duration of the event at each level of intensity to be performed. Adverse events characterized as intermittent require documentation of the onset and duration of each episode. Changes in the assessment of relationship to the Test Article shall also be clearly documented.

Subjects who present with an adverse event shall be followed by the Investigator, within licensure, until all signs and symptoms have returned to pre-treatment status, stabilized, or been satisfactorily resolved. If further treatment beyond licensure is required, the patient will be referred to the appropriate health care provider. The Investigator will use his/her clinical judgment as to whether a subject reporting with an adverse event will continue in the study. If a subject is discontinued from the study, it will be the responsibility of the Investigator to record the reason for discontinuation. The Investigator will also document the adverse event appropriately and complete the Adverse Event eCRF. Any subjects with ongoing adverse events related to the test article, study treatment or study procedures, as of the final study visit date, should be followed to resolution of the adverse event or until referral to an appropriate health care provider, as recommended by the Investigator. Non-ocular adverse events that are not related to the test article, study treatment, or study procedures may be recorded as "ongoing" without further follow-up.

#### 13.4. Reporting Adverse Events

The Investigator will notify the Sponsor of an adverse event by e-mail, facsimile, or telephone as soon as possible and no later than 24 hours from discovery for any serious /significant adverse events, and 2 days from discovery for any non-significant adverse event. In addition, a written report will be submitted by the Principal Investigator to the IEC/IRB according to their requirements (Section 13.4.2). The report will comment whether the adverse event was considered to be related to the test article, study treatment or study procedures.

#### 13.4.1. Reporting Adverse Events to Sponsor

#### **Serious/Significant Adverse Events**

The Investigator will inform the sponsor of all serious/significant adverse events occurring during the study period as soon as possible by e-mail, fax, or telephone, but no later than 24 hours following discovery of the event. The Investigator is obligated to pursue and obtain information requested by the Sponsor in addition to that information reported on the eCRF. All

subjects experiencing a serious/significant adverse event must be followed up and all outcomes must be reported.

When medically necessary, the Investigator may break the randomization code to determine the identity of the treatment that the subject received. The Sponsor and study monitor should be notified prior to unmasking the test articles.

In the event of a serious/significant adverse event, the Investigator must:

- Notify the Sponsor immediately.
- Obtain and maintain in the subject's records all pertinent medical information and medical judgment for colleagues who assisted in the treatment and follow-up of the subject.
- Provide the Sponsor with a complete case history which includes a statement as to whether the event was or was not related to the use of the test article.
- Notify the IEC/IRB as required by the IEC/IRB reporting procedure according to national regulations.

## **Unanticipated (Serious) Adverse Device Effect (UADE)**

In the event of an Unanticipated (Serious) Adverse Device Effect (UADE), the Investigator will submit a report of the UADE to the Sponsor and IEC/IRB as soon as possible, but no later than 24 hours after the Investigator first learns of the effect. This report is in addition to the immediate notification mentioned above.

The Sponsor must conduct an evaluation of the UADE and must report the results of the evaluation to FDA, the IEC/IRB and participating Investigators within 10 working days after the Sponsor first receives notification of the effect.

#### **Non-Serious Adverse Events**

All non-serious adverse events, including non-serious adverse device effects, will be reported to the sponsor by the Investigator no later than 2 days from discovery.

## 13.4.2. Reporting Adverse Events to the Responsible IEC/IRB and Health Authorities

Adverse events that meet the IEC/IRB requirements for reporting must be reported within the IEC/IRB's written guidelines. Each clinical site will refer to and follow any guidelines set forth by their Approving IEC/IRB. Each clinical site will refer to and follow any guidelines set forth by their local governing Health Authorities.

The Sponsor will report applicable Adverse Events to the local health authorities according the written guidelines, including reporting timelines.

#### 13.4.3. Event of Special Interest

Not applicable

#### 13.5. Reporting of Pregnancy

Subjects reporting pregnancy (by self-report) during the study will be discontinued after the event is recorded as an Adverse Event. Once discontinued, pregnant participants and their fetuses will not be monitored for study related purposes.

Pregnant participants are not discontinued from contact lens or solution related studies for safety concerns, but due to general concerns relating to pregnancy and contact lens use. Specifically, pregnant women are discontinued due to fluctuations in refractive error and/or visual acuity that occur secondary to systemic hormonal changes, and not due to unforeseen health risks to the mother or fetus.

#### 14. STATISTICAL METHODS

#### 14.1. General Considerations

Statistical Analysis will be undertaken by the sponsor or under the authority of the sponsor. A general description of the statistical methods to be implemented in this clinical trial is outlined below. All data summaries and statistical analyses will be performed using the SAS software Version 9.4 or higher (SAS Institute, Cary, NC). Throughout the analysis of data, the results for each subject/eye will be used when available for summarization and statistical analysis. Unscheduled visits will be summarized separately and will be excluded from the statistical analysis.

Summary tables (descriptive statistics and/or frequency tables) will be provided for all baseline variables, efficacy variables and safety variables as appropriate. Continuous variables will be summarized with descriptive statistics (n, mean, standard deviation [SD], median, minimum and maximum). Frequency count and percentage of subjects or eyes within each category will be provided for categorical data.

#### 14.2. Sample Size Justification

This study was designed and powered to test for non-inferiority of the Test relative to the Control with respect to Distance Monocular Visual Acuity (logMAR) post lens fitting under the lighting conditions, low luminance high contrast and high luminance low contrast. Historical data from was utilized for the sample size calculation since this study used the same control lens (1-Day Acuvue Define Vivid Style). Was a dispensing, 4-visit, 2×2 crossover where, 313 subjects were enrolled with 282 completing the study. However, visual acuity was only collected post lens fitting. Table 4 below contains the summary of visual acuity (logMAR) by lighting condition and lens type.

Table 4: Descriptive Summary of Distance Monocular Visual Acuity (logMAR)

Lens Type	High Luminance Low Contrast	Low Luminance High Contrast
Control -Mean	0.0474 (0.09041)	0.0851 (0.09454)
$(SD^1)$		

<sup>1SD: Standard Deviation

Since the Test and Control lenses have not been utilized in the same study, it was assumed for the sample size calculation that there was no difference between the Test and Control lenses and that both study lenses have similar variation with respect to visual acuity for both lighting conditions and that there was a perfect correlation between the left and right eyes. Furthermore, a conservative estimate of 0.30 was used for the intraclass correlation between periods, providing a sample size estimate based on the "worst-case" scenario. The sample size was calculated using a two-sided type I error rate of 5% to achieve a minimum power of 80%. The calculation was performed using the POWER Procedure in SAS Version 5.1. Table 5 below contains the sample size to test for non-inferiority of the Test relative to the Control for each lighting condition.

Table 5: Sample Size Calculation to Test for Non-Inferiority – Visual Acuity

	Minimum Number of	
Lighting Condition	Subjects to Complete	Power (%)
High Luminance Low	30	80.4
Contrast		
Low Luminance High	33	80.7
Contrast		

As shown in the table above, to meet both primary hypotheses a minimum of 33 subjects are required to complete the study. Since this is 2×2 crossover we will aim to complete 34 subjects with equal allocation between the 2 lens wear sequences. To adjust to subject dropout, approximately 40 subjects will be enrolled to ensure that at least 34 subjects complete the study.

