#### 2.3. Hypotheses

**Primary Hypotheses** 

Both primary hypotheses must be met in order to satisfy the objective of the study.

- 1. The Test lens will be non-inferior to the Control lens with respect to high luminance low contrast Distance Monocular Visual Acuity (logMAR) post lens fitting. A non-inferiority margin of 0.05 logMAR will be used.
- 2. The Test lens will be non-inferior to the Control lens with respect to low luminance high contrast Distance Monocular Visual Acuity (logMAR) post lens fitting. A non-inferiority margin of 0.05 logMAR will be used.

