## Distance Monocular Visual Acuity (logMAR)

Distance monocular visual acuity will be analyzed using a linear mixed model post lens fitting. Sequence of lens wear, lens, period, lighting condition and the interaction between lens by lighting condition will be included in the model as fixed effects. Other baseline characteristics such as age, gender and race may be included in the model when necessary. Subject and eye nested within subject will be included as random effects. Residual errors from measurements between lighting conditions within the same period will be model using one of the following covariance structures:

- Unstructured (UN)
- Compound Symmetry (CS)
- Heterogenous Compound Symmetry (CSH)

The structure that returns the lowest finite sample corrected Akaike's Information criterion will be selected as the structure that best fits the model. The Kenward and Roger method will be used for the denominator degrees of freedom.

Comparisons between the Test and Control post lens fitting will be carried out separately for each lighting condition using 2-sided 95% confidence intervals for the least-square mean (LSM) difference (Test minus Control). Adjustments for multiple comparisons will be conducted using a Bonferroni approach.

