## **Hypothesis:**

The null and alternative hypothesis for visual acuity to test for non-inferiority of the Test lens relative to the Control lens is as follows:

$$H_o$$
:  $\mu_T - \mu_C \ge 0.05$   
 $H_A$ :  $\mu_T - \mu_C < 0.05$ 

Where  $\mu_T$  and  $\mu_C$  represent the populations means for distance monocular visual acuity for the Test and Control lenses, respectively. Non-inferiority will be tested separately for each lighting condition. Non-inferiority will be declared if the upper limit of each 95% confidence interval for the LSM difference between the Test and Control is below 0.05. i.e. P( $\mu_T - \mu_C < 0.05$ )  $\geq 0.975$ .

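### Table 5's 80% power holds only at a one-sided 5% level; under the plan's two-sided 95% interval rule the same sample sizes give about 70%

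*Combined protocol and SAP*

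**What the plan says.** Section 14.2 describes the sizing: "The sample size was calculated using a two-sided type I error rate of 5% to achieve a minimum power of 80" per cent. The same section assumes that "there was no difference between the Test and Control lenses", that both lenses vary alike, and that the two eyes are perfectly correlated. It adds that "a conservative estimate of 0.30 was used for the intraclass correlation between periods" and calls this a worst case. The SDs come from the Control lens in a historical crossover (Table 4): 0.09041 for high luminance low contrast and 0.09454 for low luminance high contrast. Section 2.3 sets the margin: "A non-inferiority margin of 0.05 logMAR will be used".

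Table 5 reports 30 completers with 80.4% power and 33 completers with 80.7% power. From this the plan concludes that 33 completers are enough for both primary hypotheses, and it sets a target of 34 completers from about 40 enrolled.

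Section 14.5 compares the lenses in each lighting condition "using 2-sided 95% confidence intervals for the least-square mean (LSM) difference (Test minus Control"). The decision rule reads: "Non-inferiority will be declared if the upper limit of each 95% confidence interval for the LSM difference" is below 0.05. The section restates that criterion as a probability of at least 0.975.

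**The concern.** A non-inferiority test uses one end of the interval. When the upper limit of a two-sided 95% interval must lie below the margin, the one-sided type I error is 2.5%. Section 14.2's two-sided 5% agrees with that, so the text of Sections 14.2 and 14.5 is consistent. The numbers in Table 5 do not fit it: they look too favourable for a 2.5% one-sided test with these SDs and this correlation, and they look right for a 5% one-sided test.

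Table 5 is the only sizing rationale in a trial labelled confirmatory. If it was computed for a more lenient test than the one to be run, the stated minimum of 80% power is not supported for either primary hypothesis. The claim that 33 completers suffice for both would then fail as well.

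**Working it through.** **Inputs**
- SDs: 0.09041 and 0.09454 (Table 4).
- Correlation between periods: 0.30; correlation between eyes: 1, so each subject contributes one paired difference; true difference: 0 (Section 14.2).
- Margin: 0.05 logMAR (Section 2.3).

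**SD of the within-subject difference**, SD × √(2 × (1 − 0.30)):
- High luminance low contrast: 0.09041 × √1.4 = 0.10697.
- Low luminance high contrast: 0.09454 × √1.4 = 0.11186.

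**Power** = 1 − F(t₁₋α,ₙ₋₁; n − 1, λ), where F is the noncentral t distribution function and λ = 0.05 × √n / SD of the difference.
- High luminance low contrast, n = 30: λ = 0.05 × √30 / 0.10697 = 2.560.
- Low luminance high contrast, n = 33: λ = 0.05 × √33 / 0.11186 = 2.568.

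**Step 1: reproduce Table 5 at one-sided 5%.**
- n = 30, critical t = 1.699: 80.37% (Table 5: 80.4%).
- n = 33, critical t = 1.694: 80.73% (Table 5: 80.7%).
- At n = 29 and n = 32, power is 79.1% and 79.6%, so 30 and 33 are exactly the smallest sizes reaching 80%.

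Both sizes and both powers match.

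**Step 2: apply the level the plan states and uses (one-sided 2.5%).**

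| | High luminance low contrast | Low luminance high contrast |
|---|---|---|
| Table 5 size and stated power | n = 30, 80.4% | n = 33, 80.7% |
| Power at that size | 69.7% (critical t 2.045) | 70.2% (critical t 2.037) |
| Power at 34 completers | 75.3% | 71.6% |
| Power if all 40 complete | 82.2% | 78.7% |
| Completers needed for 80% | 38 (80.1%) | 42 (80.7%) |

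**Step 3: look for another explanation of Table 5.** With the same inputs:
- Normal approximation at one-sided 2.5%: 72.6% and 72.8%.
- Two one-sided tests (equivalence), each at 5%: 60.9% and 61.6%.
- Parallel-group t-test at one-sided 5%, with n per arm: 68.2% and 68.5%.
- Taking n − 2 degrees of freedom for the crossover moves power by no more than about 0.2 points.

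None of the alternatives matches. Table 5's powers at one-sided 2.5% would need a between-period correlation of about 0.46 rather than 0.30.

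**The case against.** The strongest reply is that the plan's assumptions are deliberately pessimistic, so true power may still reach 80%. The correlation of 0.30 is presented as a worst case. Perfect correlation between eyes gives no credit for the second eye, although the planned mixed model uses both. At one-sided 2.5% and 34 completers, an assumed between-period correlation of 0.50 would give about 88% and 85%. Keeping 0.30, 80% would also be reached if the Test-minus-Control differences in the two eyes were correlated at no more than about 0.78 (high luminance low contrast) or 0.63 (low luminance high contrast). The documents give none of these correlations, so true power is unknown, not shown to be below 80%. That stands as a limit on the claim. It does not rescue Table 5, which is presented as the result of the stated inputs at the stated level and is not.

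It is also fair that 34 completers, not 30 or 33, is the planned size. Power there is 75.3% and 71.6%, so the shortfall is smaller for high luminance low contrast, but both conditions remain below 80%. Type I error and the estimate are indeed unaffected; the cost is a higher chance of an inconclusive trial.

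Two other features of the plan can only lower power further. Section 2.3 requires both hypotheses to be met, so joint power at 34 completers cannot exceed 71.6%; it would be about 54% if the two endpoints were independent (0.7534 × 0.7156 = 0.539). Sections 14.4 and 14.5 also mention a Bonferroni adjustment. If that governed the decision (one-sided 1.25%), power at 34 would be 64.8% and 60.5%.

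**Conclusion.** The concern holds. Table 5 matches a one-sided 5% calculation, whereas Sections 14.2 and 14.5 specify a test at one-sided 2.5%. Under the plan's own assumptions, power is overstated by 10.7 points at n = 30 (80.4 − 69.7) and 10.5 points at n = 33 (80.7 − 70.2). At the planned 34 completers it is 75.3% and 71.6%. The type II risk in the limiting condition is 28.4% at 34 completers (29.8% at 33), against the 19.3% that Table 5 implies. Even with no dropout among 40 enrolled, low luminance high contrast stays just under 80%.

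These figures rest on zero true difference, the Table 4 SDs applied to both lenses, a between-period correlation of 0.30 and perfect correlation between eyes. Because this is the stated sizing basis of a confirmatory trial, it must be corrected.

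**What to change.** Recalculate Section 14.2 and Table 5 at one-sided 2.5%, matching the rule in Section 14.5, and name that level explicitly. Then take one of three routes:

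- **Restate power.** Keep 34 completers and report about 75% and 72% under the stated assumptions. This costs wording and one recalculation, with no added subjects; the stated power becomes less favourable.
- **Justify another correlation.** If the historical 2×2 crossover (282 completers) yields a usable between-period correlation, use it and report it. At 34 completers, about 0.38 gives 80% for high luminance low contrast, and 0.43 gives at least 80% for both. The documents do not show that value, so it has to be produced, not assumed.
- **Raise the target.** Under the current assumptions, 80% for each condition needs 42 completers, with enrolment above 40 to allow for dropout.

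Whichever route is taken, 80% should not be claimed at a correlation of 0.30 with 34 completers. The revised text should also give power for meeting both hypotheses together and say whether the Bonferroni-adjusted or unadjusted interval decides. The analysis should not be moved to a 90% interval to fit Table 5, because that would loosen the confirmatory criterion in Section 14.5.

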## 14.4. Level of Statistical Significance

All planned analysis for this study will be conducted with an overall type I error rate of 5%. Both adjusted and unadjusted confidence intervals will be reported. For the adjustment of multiple comparisons, a Bonferroni approach will be used.

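### The 33 subjects said to be needed for both primary hypotheses is only the larger single-hypothesis size; joint power at 34 completers is about 54% to 67% under the stated 95% interval rule

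*Combined protocol and SAP*

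**What the plan says.** Section 2.3 makes success conjunctive: "Both primary hypotheses must be met in order to satisfy the objective of the study". The two hypotheses are non-inferiority with a 0.05 logMAR margin under high luminance low contrast (HLLC) and under low luminance high contrast (LLHC).

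Section 14.2 states that "The sample size was calculated using a two-sided type I error rate of 5% to achieve a minimum power of 80" per cent. Table 5 gives each lighting condition its own size and power: 30 completers and 80.4% for HLLC, 33 completers and 80.7% for LLHC. The text then concludes that "to meet both primary hypotheses a minimum of 33 subjects are required to complete the study", rounds up to 34 for balance between sequences, and plans to enrol about 40.

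The calculation assumes no true difference between lenses. It also states that "a conservative estimate of 0.30 was used for the intraclass correlation between periods" and that "there was a perfect correlation between the left and right eyes".

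Section 14.5 declares non-inferiority when the upper limit of each 95% interval is below 0.05. Section 14.4 adds that "Both adjusted and unadjusted confidence intervals will be reported", and Section 14.5 that "Adjustments for multiple comparisons will be conducted using a Bonferroni" approach. The decision rule does not say which set of intervals it uses.

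**The concern.** When both tests must succeed, the chance of overall success is never above the smaller of the two separate powers, and falls below it unless the endpoints are almost perfectly correlated. Taking the larger single-endpoint size therefore does not carry its power over to the joint requirement. The plan states neither a joint power nor a correlation between the two lighting conditions, so the probability of the only success it recognises is missing.

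The plan does not say in words that joint power is 80%. But it sets an 80% minimum and then names 33 as the number for meeting both hypotheses. A reader of this confirmatory study could easily take the Table 5 figures as its chance of success, which would overstate it.

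**Working it through.** **Inputs from the plan.** SDs 0.09041 (HLLC) and 0.09454 (LLHC), from Table 4; period correlation 0.30, between-eye correlation 1 and true difference 0, from Section 14.2; margin 0.05, from Section 2.3; 34 completers.

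**Assumed.** The correlation between the two endpoints' Test minus Control differences, taken as 0, 0.5 and 0.9.

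**SD of the within-subject difference** = SD × √(2 × (1 − 0.30)):
- HLLC: 0.09041 × √1.4 = 0.1070
- LLHC: 0.09454 × √1.4 = 0.1119

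**Single-endpoint power.** Noncentral t with n − 1 degrees of freedom and noncentrality 0.05 × √n / SD of the difference.

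*Reproducing Table 5.* The noncentrality is 2.560 for HLLC at n = 30 and 2.568 for LLHC at n = 33.
- One-sided 5%: 80.4% and 80.7%, matching Table 5 to the decimal.
- One-sided 2.5%, which is what two-sided 5% and a 95% interval imply: 69.7% and 70.2%, which do not match.

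Table 5 therefore rests on one-sided 5%, not on the stated level.

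*At n = 34* the noncentrality is 2.725 (HLLC) and 2.606 (LLHC):

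| One-sided alpha per endpoint | HLLC | LLHC |
|---|---|---|
| 5% (reproduces Table 5) | 84.7% | 81.8% |
| 2.5% (unadjusted 95% interval) | 75.3% | 71.6% |
| 1.25% (Bonferroni interval) | 64.8% | 60.5% |

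**Joint power at n = 34.** At zero correlation it is the product of the two powers: 0.847 × 0.818 = 0.693; 0.753 × 0.716 = 0.539; 0.648 × 0.605 = 0.392. For other correlations I simulated bivariate normal mean differences with a Wishart covariance matrix and counted trials with both upper limits below 0.05. The ceiling is the smaller single-endpoint power.

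| One-sided alpha | Corr. 0 | Corr. 0.5 | Corr. 0.9 | Ceiling |
|---|---|---|---|---|
| 5% | 69.3% | 73.1% | 78.5% | 81.8% |
| 2.5% | 53.9% | 59.7% | 67.2% | 71.6% |
| 1.25% | 39.2% | 46.5% | 55.4% | 60.5% |

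At one-sided 5%, joint power reaches 80% only at a correlation of about 0.96. At 33 completers it is 67.5%, 71.6% and 77.3% (one-sided 5%), or 51.9%, 58.0% and 65.7% (95% interval).

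**Separating the two causes**, starting from 81.8% at n = 34, for correlations 0, 0.5 and 0.9:
- Joint requirement at Table 5's alpha: 12.5, 8.7 and 3.3 points.
- Moving to the 95% interval rule after that: a further 15.4, 13.4 and 11.3 points.

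The split depends on the order. Within the 95% interval rule, the joint requirement costs 17.7, 11.9 and 4.4 points from 71.6%.

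**Sensitivity to the conservative inputs (n = 34).** A between-eye correlation r of the differences below 1 multiplies the SD of the two-eye mean by √((1 + r)/2). Values are for endpoint correlations 0, 0.5 and 0.9.

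| | 95% interval rule | One-sided 5% |
|---|---|---|
| Joint power at r = 0.7 (assumed) | 64%, 69%, 75% | 78%, 80%, 84% |
| r at or below which joint power reaches 80% | 0.29, 0.36, 0.51 | 0.62, 0.71, 0.93 |
| Period correlation giving 80% joint power, with r = 1 | 0.55, 0.52, 0.47 | 0.43, 0.40, 0.33 |

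**The case against.** The strongest reply is that nothing is miscalculated: 33 is correctly the larger of 30 and 33, Table 5 is labelled as per lighting condition, and the plan never claims 80% joint power. That stands as a description of Table 5. It does not rescue the sentence that turns the larger size into the number for meeting both hypotheses.

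Second, 54% to 67% mixes the joint requirement with a separate alpha mismatch. This is fair, and the two are split above. Correcting the alpha alone would still leave the joint loss.

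Third, the inputs are deliberately pessimistic. The plan calls its period correlation conservative and the result a worst case, and its model uses data from each eye. At an assumed period correlation of 0.5, joint power at 34 is 75%, 78% and 82% under the 95% interval rule and 86%, 87% and 90% at one-sided 5%. So the figures are power on the plan's own inputs, not a forecast. The plan does not show that more favourable correlations apply.

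Fourth, 34 is a floor and about 40 will be enrolled. Even 40 completers give only 65%, 69% and 75% under the 95% interval rule (78%, 81% and 85% at one-sided 5%). Forty is also an upper bound on enrolment as planned, because Section 4.3 counts enrolment from consent and screen failures are therefore included.

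**Conclusion.** The concern holds. On the plan's own inputs and its stated two-sided 5% and 95% interval rule, 34 completers give joint power of about 54%, 60% and 67% for assumed endpoint correlations of 0, 0.5 and 0.9. The 80% minimum is out of reach at every correlation, because LLHC alone has 71.6%. At the one-sided 5% that reproduces Table 5, joint power is 69%, 73% and 79%, so the joint requirement matters even without the alpha problem. If Bonferroni intervals governed, it would be 39%, 46% and 55%.

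These results rest on a period correlation of 0.30, perfect between-eye correlation and no true difference. A higher period correlation or a lower between-eye correlation would raise them.

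**What to change.** 1. Reword the sentence in Section 14.2: 33 is the larger of the two single-hypothesis sizes, and the 80% target applies to each hypothesis separately.
2. Reconcile the one-sided 5% behind Table 5 with the stated two-sided 5% and the 95% interval rule.
3. State in Section 14.5 that the unadjusted 95% intervals govern the decision. Because both hypotheses must be met, no multiplicity adjustment is needed to control the type I error. If the Bonferroni intervals are meant to govern, recompute the power.
4. Add a row to Table 5 with joint power at 34 completers under the governing rule, over a stated range of endpoint correlations.
5. Note that the figures depend on the period and between-eye correlations, and in which direction. The historical crossover can inform these only as a proxy, since "the Test and Control lenses have not been utilized in the same study".

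The cost is text only: one reworded sentence, one alpha correction, one sentence naming the interval, one table row and one caveat. No extra subjects are requested. The visible consequence is that 80% becomes a per-hypothesis figure, with a lower one beside it for both.
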